3.10. Data Handling Conventions

Treatment of lab data transformations, handling of missing dates for AE and concomitant medication analysis, and other data handling conventions are described in the TLF shells document.

4. SUBJECT DISPOSITION

4.1. Subject Enrollment and Disposition

The number of subjects who are screened, randomized, and included in each analysis set will be presented. Patients who received study treatment, completed or discontinued from the study treatment will be presented based on the number of patients in each treatment group and overall for each study phase. Reasons for not completing the study or treatment will be summarized for each treatment group and for each study phase.

A summary of subject enrollment will be provided by treatment groups for individual investigators within each country, and overall based on the all subjects randomized set.

A similar enrollment table will be provided by randomization stratum based on the all subjects randomized set. The strata used for the randomization are as follows:

- Concomitant use of approved IPF therapy (yes vs no)
- FVC% predicted ($\geq 70 \text{ vs} < 70\%$)
- Prior use of approved IPF therapy (yes vs no)

The denominator for the percentage of subjects in the stratum will be the total number of randomized subjects in applicable treatment group and overall. If there are discrepancies in the value used for stratification assignment between the Interactive Response Technology (IRT) and the clinical database, the value collected in IRT will be used in efficacy analysis. A listing of subjects with discrepancies in the value used for stratification assignment between the IRT and the clinical database at the time of data finalization will be provided.

The randomization schedule used for the trial will be provided as an appendix to the CSR.

4.2. Extent of Study Drug Exposure and Compliance

Extent of exposure to study drug will be examined by assessing the total duration of exposure to study drug and the level of adherence to the study drug specified in the protocol for each study phase and combined periods.

4.2.1. Duration of Exposure to Study Drug

Total duration of exposure to study drug, defined as last dosing date minus first dosing date plus 1, regardless of any temporary interruptions in study drug administration, will be summarized by treatment groups using descriptive statistics. Handling of missing last study drug dosing date will be described in the TLF shells document.

Version 2.0

4.2.2. Compliance to Study Drug

The total number of doses administered will be summarized as continuous variables using descriptive statistics. Additionally, the total number of doses administered per subject will be summarized as a frequency distribution.

The presumed total number of doses administered to a subject will be determined by the data collected on the drug accountability CRF using the following formula:

Total Number of Doses Administered =

$$\left(\sum No. \text{ of Doses Dispensed}\right) - \left(\sum No. \text{ of Doses Returned}\right)$$

4.2.2.1. On-Treatment Adherence

The level of on-treatment adherence to the study drug regimen will be determined by the total amount of study drug administered relative to the total amount of study drug expected to be administered during a subject's actual on-treatment period based on the study drug regimen.

The level of on-treatment adherence will be expressed as a percentage using the following formula:

On-Treatment Adherence (%) =
$$\left(\frac{\text{Total Amount of Study Drug Administered}}{\text{Study Drug Expected to be Administered on Treatment}}\right) \times 100$$

Descriptive statistics for the level of on-treatment adherence with the number and percentage of subjects belonging to adherence categories (<80%, 80 - 120%, >120%) will be provided by treatment group.

No formal statistical testing is planned.

A by-subject listing of study drug administration (including both randomized and actual drug dispensed) and a separate drug accountability listing will be provided by subject ID number and visit. A listing of overall adherence will be provided as well, including any reasons for interruption of treatment.

4.3. Protocol Deviations

Protocol deviations (PDs) occurring after subjects entered the trial are documented during routine monitoring. The number and percentage of subjects with major protocol deviations by deviation reason and subjects with protocol deviations related to COVID-19 will be summarized by treatment group for each study phase. A by-subject listing will be provided for eligibility criteria deviations and all other protocol deviations.

5. BASELINE CHARACTERISTICS

Demographics, baseline characteristics and medical history will be summarized on the FAS and Safety analysis set for the Core Phase and OLE-SAF set for the OLE Phase.

5.1. Demographics

Subject demographic variables (ie, age, sex, race, and ethnicity) will be summarized by treatment group and overall using descriptive statistics for age, sex, race, [age category <18, 18 - <65, $65 - \le 75$, >75], and ethnicity.

A by-subject demographic listing, including the informed consent date, will be provided by subject ID number in ascending order by treatment group.

5.2. Baseline Characteristics

Baseline characteristics include body weight (in kg), height (in cm), body mass index (BMI; in kg/m²), child-bearing potential (yes, no, not applicable), regions subjects were enrolled, and the stratification factors collected in the clinical database as well as in the IRT system will be summarized by treatment group. The stratification factors used for randomization are:

- The prior use of approved IPF therapy (i.e., nintedanib or pirfenidone, yes or no, stratification factor before Protocol Version 4.0)
- Concomitant use of approved IPF therapy (i.e., nintedanib or pirfenidone) (yes or no)
- FVC% predicted at Baseline ($\geq 70, <70$)

Additional IPF history variables include: screening HRCT scan presence of: 10% - <50% parenchymal fibrosis (reticulation), <25% honeycombing, or extent of fibrotic changes being greater than the extent of emphysema, baseline FVC % predicted categories (<45%, 45% - 80%, >80%), baseline forced expiratory volume in 1 second (FEV1)/FVC% predicted categories (<0.7 and ≥0.7), and DLCO corrected for hemoglobin categories (<25%, 25-90%, >90%).

These baseline characteristics and IPF history variables will be summarized by treatment group and overall using descriptive statistics for continuous variables and using number and percentage of subjects for categorical variables.

A by-subject listing of the above baseline characteristics will be provided by treatment group and subject ID number in ascending order.

A by subject listing of subjects' substance abuse data will be provided by subject ID and treatment group.

Version 2.0

5.3. Medical History

Medical history will be collected at screening for disease-specific and general conditions (ie, conditions not specific to the disease being studied).

Medical history will be coded using the current version of the Medical Dictionary for Regulatory Activities (MedDRA), summarized and presented overall for the Safety Analysis Set by treatment group. Summaries will be presented alphabetically by system organ class (SOC) and, within a SOC, alphabetically by preferred term.

6. EFFICACY ANALYSES

6.1. Core Phase

6.1.1. Primary Efficacy Endpoint

6.1.1.1. Primary Analysis Method

The primary efficacy endpoint is the change from Baseline in FVC % predicted at Week 52. The FVC% predicted data are collected at Screening, Day 1, Week 4, Week 16, Week 28, Week 40, and Week 52.

The estimand for the primary efficacy analyses is constructed to compare the primary endpoint between each dose regimen of HZN-825 and placebo, using the treatment policy strategy approach to ICEs without data imputation in FAS subjects.

The primary analysis will be based on a mixed model for repeated measures (MMRM) analysis of covariance (ANCOVA) model using observed change in FVC % predicted values from all planned post-baseline assessments (Weeks 4, 16, 28, 40 and 52) with covariates of treatment group (300 mg HZN-825 QD, 300 mg HZN-825 BID, placebo), prior use of IPF therapy [yes or no], FVC% predicted at baseline [≥ 70, <70], visit week, and treatment by visit week interaction. An unstructured covariance matrix will be used as the primary analysis method; if the model does not converge, the following three variance-covariance matrices or by visit week will be attempted in order until one converges: heterogeneous Toeplitz (TOEPH), heterogeneous compound symmetry (CSH), and Toeplitz (TOEP).

Treatment group least squares means, associated standard error (SE) and their differences (each HZN-825 group minus placebo separately), SE of the difference, 90% CIs and p-values for each visit will be provided with Week 52 estimands being the primary efficacy endpoint result. A line plot of the LS mean value for FVC% predicted change from Baseline will be plotted by treatment group for each visit week over time, including the estimated 90% CI around each LS mean.

Change in FVC % predicted will also be summarized descriptively for observed cases at each visit.

6.1.1.2. Intercurrent Event Strategies

Potential intercurrent events (ICEs) such as early discontinuation from the treatment, rescue therapy uses during treatment, death, lung transplant, may occur during the trial.

Subjects who experience any of the ICEs including subjects with early discontinuations from treatment will be encouraged to stay in the trial after those ICEs occur, and data will be collected through planned study completion. In general, treatment policy strategy will be used to account for the ICEs for efficacy endpoints.

Version 2.0

The estimand framework is summarized for the primary endpoint in Table 2.

Table 2. Estimand Framework for Primary Endpoint

Endpoint	Treatment	Population	Intercurrent Events (ICE) & ICE Strategy	Population-Level Summary
Change	HZN-825 300	The Full	The intercurrent events which may impact	Point estimate (The
from	mg BID,	Analysis Set	analysis results include discontinuing from	least squares mean [LS
Baseline in	HZN-825 300		the treatment, initiating rescue therapy	mean] difference for
FVC %	mg QD and		during treatment, death, lung transplant	the change from
predicted at	Placebo			Baseline to Week 52
Week 52			The treatment policy strategy will be used for aforementioned intercurrent events, which will closely reflect the real-world situation. All observed data will be used without missing data imputation. A mixed model for repeated measures	based on MMRM mixed model with its 90% confidence interval and P-value.
			(MMRM) will be fit to the data for the	
			observed changes in FVC % predicted	
			values from all planned post-baseline visits	
			(Weeks 16, 28, 40 and 52). The least	
			squares mean (LS mean) difference for the	
			change from Baseline at Week 52 will be	
			estimated from this model.	

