# 9.6.1.3 Primary Efficacy Endpoint Analysis

The estimand for the primary efficacy analyses will be constructed to compare the primary endpoint between each dose regimen of fipaxalparant (HZN-825) and placebo using the treatment policy strategy approach to intercurrent events. All subjects who are randomized and take at least 1 dose of trial drug will be included in the primary efficacy analyses (FAS).

The primary efficacy endpoint will be change from Baseline in FVC % predicted to Week 52. A mixed model for repeated measures (MMRM) analysis of covariance model will be fit to the data using observed change in FVC % predicted values from all planned post-Baseline assessments (i.e., Weeks 4, 16, 28, 40, and 52) with covariates of stratification factors (concomitant use of IPF therapy [yes, no] and FVC % predicted at Baseline [≥70%, <70%]), treatment group, visit and visit-by-treatment group interaction. The unstructured variance-covariance matrix will be used in the model. Treatment group least squares means, associated standard error (SE) and their differences (each fipaxalparant [HZN-825] group minus placebo separately), SE of the difference, 90% CIs and p-value overall and for each visit will be provided.

For subjects with missing data at 1 or more time points, the available data will be included in the analysis.

As a supplemental analysis to assess the robustness of the efficacy analysis results, the effect of each dose regimen of fipaxalparant (HZN-825) will be compared to placebo using the following measurements and methods:

Horizon Therapeutics Ireland DAC (a wholly owned subsidiary of Amgen Inc.) Date: 07 October 2024

IND 154671

Fipaxalparant (HZN-825) Protocol: HZNP-HZN-825-303 Version 5.0, Amendment 4

- Change in FVC (in mL) from Baseline to Week 52 using a similar MMRM analysis method as described for the primary efficacy endpoint
- Cumulative response curve comparison using the Kolmogorov-Smirnov test on:
  - The range of improvement (≥0% to ≥15% with a 5% increment) and worsening (< -15% to <0% with a 5% increment) based on the change in FVC % predicted value from Baseline at Week 52

  - The range cut-off values from less than -300 mL to greater 100 mL with a 100-mL increment based on the change in FVC (in mL) from Baseline at Week 52

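### SAP Table 2 omits Week 4 from the primary MMRM visit list, against SAP 6.1.1.1, SAP Table 1 and protocol 9.6.1.3: a minor correction to make before unblinding

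*SAP*

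**What the plan says.** SAP 6.1.1.1 (Primary Analysis Method) fits the primary MMRM to change in FVC % predicted at "Weeks 4, 16, 28, 40 and 52". It states that "The FVC% predicted data are collected at Screening, Day 1, Week 4, Week 16, Week 28, Week 40, and Week 52". It also gives the covariates, the treatment-by-visit term, the covariance structure ("An unstructured covariance matrix will be used as the primary analysis method") and the fallback structures.

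SAP 6.1.1.2, Table 2, sets out the estimand framework for the same endpoint. It fits the MMRM to "values from all planned post-baseline visits", names these as "Weeks 16, 28, 40 and 52", and takes the Week 52 LS mean difference as "estimated from this model". In the same cell it says "All observed data will be used without missing data imputation".

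SAP 3.8, Table 1, gives Week 4 its own window for the primary endpoint (Day 2 to 71, target Day 29). The Week 16 window opens on Day 72.

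Protocol 9.6.1.3 specifies the primary MMRM on all planned assessments, "i.e., Weeks 4, 16, 28, 40, and 52", and the synopsis has the same list. SAP 2.5, which records departures from the protocol's planned analyses, does not mention dropping Week 4.

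**The concern.** Table 2 is where the SAP ties together the primary population, the intercurrent-event strategy, the estimator and the summary measure. Its visit list disagrees with the method section. It also disagrees with its own wording, because Week 4 is a planned FVC visit with observed data.

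The list decides who contributes. In an MMRM, a subject with only a Week 4 value still informs the Week 52 contrast through the covariance between visits. With Week 4 removed, that subject has no outcome row and leaves the analysis despite belonging to the full analysis set. These subjects are early leavers, whom a treatment-policy analysis on all observed data means to keep.

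The primary result also feeds other analyses. The multiple-imputation sensitivity analyses and several supplementary analyses reuse the primary model. Testing is hierarchical, so the BID comparison gates the QD comparison and the key secondary endpoint. The four-visit list is not visibly garbled either: it matches the Core Phase schedule for the patient-reported outcomes, so a programmer could take it as intended.

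**Working it through.** **1. The plan's own figures.** SAP 1.3 and protocol 9.6.3 assume 45 subjects per group, SD 9 and a true difference of 3. The standard error is 9 × √(2/45) = 1.897, and P(observed difference > c) = 1 − Φ((c − true difference)/1.897).

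- c = 1, true 3: Φ(1.054) = 0.854 (stated 85%)
- c = 2, true 3: Φ(0.527) = 0.701 (stated 70%)
- c = 2, true 0: 1 − Φ(1.054) = 0.146 (stated 15%)

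All three reproduce, and none uses the visit list.

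**2. The two lists as models.** An unstructured covariance for T visits has T(T+1)/2 parameters: 15 for five visits and 10 for four.

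**3. Who is lost without Week 4.** SAP 3.8 maps every observation, unscheduled ones included, by study day. Subjects who leave are asked to return for the Week 52 assessments, which include spirometry. An exit FVC from Day 72 onward falls in the Week 16 window or later and stays in both models. Only subjects with no FVC after Day 71 drop out.

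**4. Size of the difference.** The documents give no dropout rate or visit correlation, so both are assumptions here. Two sets were used, each fitting the same simulated data with and without Week 4.

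*Set A: REML MMRM with estimated unstructured covariance, treatment-by-visit terms and two stratum main effects.* There were 45 subjects per arm, with a linear decline of 5 points by Week 52 on placebo. The benefit rose linearly to 3 points, and the Week 52 SD was 9 (random slope plus visit error of SD 3.5). Dropout was monotone and unrelated to FVC. In the three dropout scenarios, 25%, 25% and 40% of leavers left straight after Week 4. Each trial gives two comparisons with placebo.

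| Dropout | Trials | Mean abs. difference | 95th percentile | SE with / without Week 4 | Decision changes | Mean subjects lost |
|---|---|---|---|---|---|---|
| 0% | 85 | 0.048 | 0.138 | 1.891 / 1.892 | 0% | 0 |
| 15% | 37 | 0.097 | 0.316 | 1.976 / 1.979 | 1.35% | 4.1 |
| 25% | 37 | 0.124 | 0.336 | 2.057 / 2.062 | 1.35% | 7.4 |
| 35% | 38 | 0.152 | 0.410 | 2.207 / 2.216 | 0% | 19.6 |

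The 1.35% is one comparison out of 2 × 37 = 74. Even with no dropout the two fits differ slightly, because the stratum effects are shared across visits.

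*Set B: generalised least squares with known covariance, no strata.* Visit SDs were 4.5, 5.5, 6.7, 7.9 and 9.0, with correlation 0.85 per visit step, a true effect of 3 and 5.5% dropout per interval.

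- Three runs of 2000, 2000 and 4000 trials gave an SD of the difference of 0.23, 0.25 and 0.25 points. The decision changed in 3.75%, 2.8% and 3.9% of trials. About 5% of subjects had only Week 4 data. The mean shift was zero, and the standard error moved from 2.079 to 2.094.
- Estimating the unstructured covariance instead (800 trials): SD 0.26, changes in 3.75%.
- Correlation 0.70 to 0.95 and dropout 3% to 9% per interval: SD 0.12 to 0.39, changes in 1.6% to 5.8%.
- Dropout 2% per interval: SD 0.14, changes in 2.2%. No dropout: no difference.
- No true effect, 5.5% dropout per interval: changes in 1.9%.

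**The case against.** The strongest reply is that nothing is truly open. Section 6.1.1.1 carries the full model, while Table 2 is introduced as a summary and gives neither covariates nor a covariance structure. Nobody could run the primary analysis from Table 2 alone, and the secondary endpoints point to 6.1.1.1 as the description of the method. Every other source includes Week 4, and Table 2's own wording contradicts its list. This reads as a dropped item. That argument stands, and it limits the point to a consistency correction.

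Three stronger readings are tempting, and the documents do not support them.

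- A reader might infer two competing definitions of the primary MMRM and a free choice between two p-values. That would mean following an incomplete summary over the method section and against the summary's own text.
- A reader might infer that everyone who leaves between Weeks 4 and 16 is lost. The Day 72 boundary and the requested exit visit keep those with an FVC after Day 71.
- A reader might take about 4% as the rate at which the decision changes. That comes from one assumed pairing of dropout and correlation; other assumptions give about 0% to 6%.

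The reply does not remove the conflict. It sits in current text, in the estimand table for the primary endpoint.

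**Conclusion.** The inconsistency is real and minor. Table 2's list conflicts with SAP 6.1.1.1, SAP Table 1, protocol 9.6.1.3 and its own description. The intended list, with Week 4, can be recovered.

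Following Table 2 literally would remove subjects with no FVC after Day 71 and could move the Week 52 result a little: typically 0.05 to 0.4 points against a standard error near 2, with the p≤0.10 decision changing in about 0% to 6% of simulated trials. The range pools mean absolute differences and SDs of the difference across the two sets. It rests entirely on assumed dropout and correlation, and Set A's change rates rest on few trials.

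No systematic bias was shown. Set A's dropout did not depend on FVC and Set B used fixed rates per interval, so these runs do not settle what happens if early leaving is related to lung function. The 85%, 70% and 15% figures are unaffected.

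**What to change.** Before unblinding, change the visit list in SAP Table 2 to "Weeks 4, 16, 28, 40 and 52", so that it matches SAP 6.1.1.1 and protocol 9.6.1.3 and the primary analysis has one definition. A cross-reference in that cell to 6.1.1.1 as the governing specification would prevent a recurrence. Record the correction in the SAP revision history. The cost is one table edit and one log entry, with no change to the sample size, the data collected or the testing order.

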6.1.1.3. Sensitivity Analyses

The following sensitivity analysis will be performed to assess the robustness of primary efficacy endpoint result.

Multiple Imputation

Multiple imputation will be carried out to impute the missing primary efficacy endpoint data based on two assumptions:

- (1) Assuming treatment effect is preserved: imputation will be done under the assumption that missing data would be similar to subjects without missing data in the respective treatment group (HZN-825 300 mg QD, HZN-825 300 mg BID, placebo). Missing data due to subject death will be imputed using the worst outcome observed among all patients with available data.
- (2) Assuming treatment effect is lost: imputation will be done under the assumption that missing data would be similar to subjects in the placebo group without missing data

Pattern mixture models (PMM) with the FCS imputation method will be used to impute missing primary efficacy endpoint in the above analyses. Missing data will be imputed based on Baseline FVC% predicted, treatment group and stratification factors used in randomization. One thousand imputed dataset will be created. For each imputed dataset, the

Version 2.0

same model as defined for the primary analysis will be used. The results from each imputed dataset will be combined using Rubin's method.

Rank ANCOVA Analysis for Death

A rank ANCOVA analysis will be performed, assigning the worst rank to patients who died before week 52 visit. Missing data for reasons other than death will be imputed assuming treatment effect is preserved in respective treatment group. The covariates included in the analysis are treatment group, prior use of IPF therapy [yes or no], FVC% predicted at baseline [≥ 70 , < 70].

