## **Efficacy**

The estimand for the primary efficacy analyses will be constructed to compare the primary endpoint between each dose regimen of fipaxalparant (HZN-825) and placebo using the treatment policy strategy approach to intercurrent events. All subjects who are randomized and take at least 1 dose of trial drug will be included in the primary efficacy analyses (FAS).

The primary efficacy endpoint will be change from Baseline in FVC % predicted to Week 52. A mixed model for repeated measures (MMRM) analysis of covariance model will be fit to the data using observed change in FVC % predicted values from all planned post-Baseline assessments (i.e., Weeks 4, 16, 28, 40, and 52) with covariates of stratification factors (concomitant use of IPF therapy [yes, no] and FVC % predicted at Baseline [≥70%, <70%]), treatment group, visit and visit-by-treatment group interaction. The unstructured variancecovariance matrix will be used in the model. Treatment group least squares means, associated standard error (SE) and their differences (each fipaxalparant [HZN-825] group minus placebo separately), SE of the difference, 90% confidence intervals (CIs) and p-value overall and for each visit will be provided.

For subjects with missing data at 1 or more time points, the available data will be included in the analysis.

One sensitivity analysis will consider whether data missing not at random may change the conclusion. A tipping point analysis will estimate the difference in true values among unobserved data that must occur to change the conclusion for each dose (i.e., change the result for each dose from p≤0.10 to p>0.10). Intercurrent events will be addressed in the primary analysis by using treatment policy strategy with all available data.

Sensitivity/supplemental analyses will assess the impact of missing data, as needed.

The key secondary endpoint will be the proportion of subjects with decline in FVC % predicted ≥10% from Baseline at Week 52 and will be analyzed using a logistic regression model with treatment group and stratified by factors used for stratifying the randomization. The logistic model will provide odds ratio, its 90% CI and p-value for comparing each fipaxalparant (HZN-825) group with the placebo group. Statistical significance for the key secondary endpoint will only be concluded if statistical significance is achieved for the primary efficacy endpoint.

IND 154671

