One sensitivity analysis will consider whether data missing not at random may change the conclusion. A tipping point analysis will estimate the difference in true values among unobserved data that must occur to change the conclusion for each dose (i.e., change the result for each dose from  $p \le 0.10$  to p > 0.10).

Potential intercurrent events such as discontinuing from the treatment, early discontinuing from the trial, initiating rescue therapy, death, lung transplant or potentially COVID-19, may occur during the trial. Intercurrent events will be addressed in the primary analysis by using treatment policy strategy with all available data. Supplemental analyses will assess the use of rescue medication. The proportion of subjects who qualify for and who receive rescue medication at each potential time point will be summarized for each treatment group to determine whether there are different use rates between treatment groups. A supplemental analysis will repeat the primary analysis except that it will ignore all FVC data collected after the initiation of rescue medication; the result will be a sensitivity analysis that uses a hypothetical strategy approach to the intercurrent even of initiation of rescue medication. A detailed plan for sensitivity/ supplemental analyses regarding potential intercurrent events including how to handle the data impacted by COVID19, will be provided in the statistical analysis plan.

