2.5. Changes from the Protocol Planned Analyses

The definition of HZN-825 Baseline has been updated from the protocol. This adjustment is essential to facilitate a comprehensive comparison of data over 104 weeks across all cohorts. As a result, HZN-825 Baseline has been redefined as the latest measurement prior to the first dose of study drug (either HZN-825 or Placebo) during the Core Phase.

For efficacy analysis, the prior use of IPF approved therapy will be used as a covariate in the mixed model for repeated measures instead of concomitant use of IPF approved therapy. In earlier protocol versions, the prior use of IPF approved therapy was used as a stratification factor, while concomitant use of IPF approved therapy was restricted. In protocol version 4, concomitant use of IPF approved therapy was permitted and used as a stratification factor. However, only a small number of enrolled subjects were on concomitant IPF therapy. To ensure a robust model estimate, the prior use of IPF approved therapy will be used in the model. Additional subgroup analysis will be conducted as needed, focusing on subjects who were on concomitant use of IPF approved therapy.

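### The imputation predictors in SAP 6.1.1.3 leave out Week 4–40 FVC and retain treatment group for the effect-lost case, and the protocol's tipping-point analysis is missing from the SAP with no record of its removal

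*SAP*

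**What the plan says.** The primary analysis (SAP 6.1.1.1) is an MMRM on observed FVC % predicted changes at Weeks 4, 16, 28, 40 and 52.

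SAP 6.1.1.3 then plans two multiple imputations, using pattern mixture models with fully conditional specification (FCS). Assumption (1) preserves the treatment effect and carries a death rule: "Missing data due to subject death will be imputed using the worst outcome observed among all patients with available data". Assumption (2) takes the effect as lost: "imputation will be done under the assumption that missing data would be similar to subjects in the placebo group without missing data". One sentence gives the predictors for both: "Missing data will be imputed based on Baseline FVC% predicted, treatment group and stratification factors used in randomization". Each imputed dataset is analysed with the primary model. A rank ANCOVA gives deaths the worst rank and adds: "Missing data for reasons other than death will be imputed assuming treatment effect is preserved in respective treatment group".

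Protocol 9.6.1.3 names a sensitivity analysis for data missing not at random: "A tipping point analysis will estimate the difference in true values among unobserved data that must occur to change the conclusion for each dose". The synopsis has the same plan and the same criterion, "change the result for each dose from p≤0.10 to p>0.10".

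SAP 6.1.1.3 and 6.1.1.4 contain no tipping-point analysis. SAP 2.5, which lists departures from the protocol, has two entries. One begins "The definition of HZN-825 Baseline has been updated from the protocol"; the other replaces concomitant with prior IPF therapy as covariate. The Version 2.0 entry in SAP Appendix 2 lists five changes, none about a tipping point.

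**The concern.** There are three linked problems.

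- **Predictors.** The MMRM allows missingness to depend on FVC seen at earlier visits. Imputation from baseline, arm and strata does not: it treats a subject who had lost 10 points by Week 40 like any other subject in that arm with the same baseline and strata. A robustness check should not need a stronger assumption than the analysis it checks. Rerunning the MMRM on the imputed data does not repair this, because Week 52 has already been filled in.
- **Effect lost.** Values meant to resemble placebo are generated from a list that contains treatment group. If arm acts as an ordinary predictor, missing active values come from the active arm and the intended dilution disappears. The death rule is written under (1) only, so deaths under (2) are undefined.
- **Tipping point.** The remaining analyses test fixed scenarios. None finds how much worse the unobserved values must be before a positive dose loses significance, which is the question the protocol set.

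At stake is whether agreement or disagreement with the MMRM can be interpreted.

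**Working it through.** **Planning figures first.** With SD 9 and 45 per arm (SAP 1.3), SE = 9 × √(2/45) = 1.90. P(observed > c) = 1 − Φ((c − δ)/SE) gives 85.4% (δ = 3, c = 1), 70.1% (δ = 3, c = 2) and 14.6% (δ = 0, c = 2). These match the stated 85%, 70% and 15%, so 1.90 is a fair yardstick.

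**Assumed scenario.** The documents give no dropout rate, visit correlation or placebo decline, so all of the following are assumptions.
- Change = subject slope × time + noise; mean decline 5 points/year, slope SD 8, residual SD 3.5.
- Week 52 SD = √(64 + 12.25) = 8.7.
- Dropout occurs after Week 40, with probability p, only in subjects already down at least 6 points.
- Baseline FVC and strata do not predict decline, so imputing on baseline and arm reproduces the arm's completer mean.

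**Closed form.**
1. Week 40 mean = −5 × 40/52 = −3.85; SD = √((8 × 40/52)² + 3.5²) = 7.08.
2. Share eligible to drop out = Φ((−6 + 3.85)/7.08) = Φ(−0.304) = 38%.
3. Regression of Week 52 on Week 40 = (64 × 40/52)/7.08² = 0.98. Expected Week 52 shortfall of eligible subjects, D = 0.98 × 7.08 × φ(0.304)/Φ(−0.304) = 6.96 points.
4. With dropout share d = 0.38p, the completer mean is too high by D × d/(1 − d).

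**Bias with no true effect and no deaths** (active minus placebo):

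| p placebo / active | Dropout | Mean decline 5 | Dropout | Mean decline 6 |
|---|---|---|---|---|
| 0.5 / 0.5 | 19% / 19% | 0.0 | 21% / 21% | 0.0 |
| 0.25 / 0.375 | 10% / 14% | 1.16 − 0.73 = +0.4 | 11% / 16% | +0.5 |
| 0.21 / 0.71 | 8% / 27% | 2.58 − 0.60 = +2.0 | 9% / 30% | +2.1 |
| 0.71 / 0.21 | 27% / 8% | −2.0 | 30% / 9% | −2.1 |

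Simulation with 400,000 per arm gives the same values. Imputing by arm from Weeks 4–40 is within 0.01 of the truth in every no-death case.

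**Death rule under (1)**, 8% versus 27%, worst outcome assumed −25. Completer means are −4.40 (placebo) and −2.42 (active). If share q of dropouts are deaths, each arm mean moves by d × q × (−25 − completer mean). The bias becomes +1.5, +0.9 or about −0.3 for q = 10%, 25% or 50%.

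**True effect 3.0, p = 0.5 in both arms.** For the active arm (mean decline 2), eligible share is 26%, d = 13%, D = 8.61 and the completer shift is 1.31. The placebo shift is 1.64.
- Arm kept in the model: 3 + 1.31 − 1.64 = 2.7.
- Placebo-only fit: (1 − 0.13) × 2.67 = 2.3.

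Under (2), keeping arm therefore returns the effect-preserved answer.

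**Effect lost with unequal rules** (p = 0.21/0.71, true effect 3; dropout 8% versus 19%). Completer means are −4.40 and −0.01, so even a placebo-only fit gives (1 − 0.19) × 4.38 ≈ 3.6. The check meant to be conservative exceeds the truth because decline before dropout is ignored.

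**A different dropout model.** With placebo change −6, true effect 3, placebo dropout 15–25%, visit correlation 0.70–0.95 and hazard rising with decline at every visit, the estimate is about 2.6–2.9 without the earlier visits and about 3.0 with them.

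**Tipping point: documents side by side.** It is in the current protocol (Version 5.0, 07 October 2024). It is also in the Version 4.0 text on which the SAP says it is based. It is not in SAP Version 2.0 (16 August 2024). The later protocol still requires it, so the two documents now conflict.

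**The case against.** - **FCS may already include the visits.** Chained equations are designed for several incomplete variables, and the imputed datasets feed a model that uses all visits, so the list could mean covariates added to the visit series. That is possible, but the text does not say it. It speaks of imputing the primary endpoint and lists the predictors.
- **Treatment group may only select placebo donors.** This is a fair reading of assumption (2), and a placebo-only fit would settle it. The SAP states no such fit, so this part is an unresolved contradiction and not proof that the program would be wrong. The 2.3 versus 2.7 gap is about 0.2 SE.
- **Some planned analyses already depart from missing at random.** True of the placebo-based imputation, the worst-outcome rule and the rank ANCOVA. None answers the tipping-point question.
- **The large biases need strong assumptions.** This stands. ±2.0 requires more than threefold different dropout among equal decliners. If baseline correlates 0.3 or 0.5 with slope, +2.0 falls to about +1.8 or +1.6. Subjects who leave are asked for Week 52 assessments, and the analysis window opens at Day 324. If a random half or three quarters of dropouts supply a value, +2.0 falls to about +0.8 or +0.4. The near-perfect recovery with Weeks 4–40 reflects dropout that depends only on Week 40 FVC, in very large samples; performance at 45 per arm is not shown.

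The tipping-point omission has no good answer in the documents.

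**Conclusion.** The concern holds, as something that should be corrected. As written, the imputation list omits collected data that the primary model uses, conflicts with the stated aim of assumption (2), and leaves deaths under (2) undefined. A protocol-required analysis is missing without explanation.

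The effect on the sensitivity results ranges from nil, when dropout does not differ selectively between arms, to about 2 points in either direction under marked differential dropout. That upper end is roughly one standard error of the difference. With a true effect and a common dropout rule, the error is modest and conservative (2.7 against 3.0). These sizes are scenarios, not forecasts. The absence of the tipping-point analysis rests on no assumption. The primary result itself is not in question.

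**What to change.** 1. Add FVC % predicted at all earlier post-baseline visits to the imputation model.
2. For assumption (1), fit by arm and keep the stated death rule.
3. For assumption (2), fit on placebo subjects only with no arm term and state how deaths are handled. Name the reference-based variant, because conditioning on a dropout's own earlier visits retains benefit already gained.
4. Use the same imputation model for non-death missing data in the rank ANCOVA.
5. Restore the tipping-point analysis with a stated delta range for each dose, or record and justify its removal in SAP 2.5 and align the protocol.

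The cost is SAP wording and modest programming. No new data are needed. A protocol change arises only if the tipping-point analysis is dropped.
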